### **9.3 Determination of Sample Size**

This Study is exploratory and its sample size is not determined by statistical power considerations, but is considered appropriate for an early phase safety trial.

### **9.4 Interim Analysis**

No formal interim analysis for efficacy is planned, as this is a study with careful monitoring of subject safety in an ongoing manner by the principal investigator, Sponsor and independent Data Safety Monitoring Board.

### **9.5 Data Quality Assurance**

The following steps will be taken to ensure the accuracy, consistency, completeness, and reliability of the data:

- Routine study site monitoring
- CRF review against source documents
- Data management quality control checks

## **10 INVESTIGATOR REQUIREMENTS**

### **10.1 Study Initiation**

Before the release of investigational products to the study site, the following documents must be on file with the sponsor:

- U.S. Food and Drug Administration (FDA) Form 1572 signed by the Principal Investigator or equivalent for non-U.S. sites if applicable.
  - The names of any sub-investigators must appear on this form. Investigators must also complete all regulatory documentation as required by local and national regulations.

- Current curricula vitae (CV) of the Principal Investigator and all subinvestigators
- Complete financial disclosure forms for the Principal Investigator and all subinvestigators
- Written documentation of Institutional Review Board (IRB)/Ethics Committee (EC) approval of the protocol (identified by protocol number or title and date of approval) and Informed Consent Form (ICF; identified by protocol number or title and date of approval)
- A copy of the IRB-approved ICF
- IRB composition or assurance letter as applicable
- Current laboratory certification of the clinical laboratory performing sample analysis, as well as current references ranges for all laboratory tests (*if applicable*)
- A Clinical Trial Agreement signed and dated by the study site
- Investigator Brochure receipt signed and dated by the Principal Investigator (*if applicable*)
- A Protocol Acceptance Form signed and dated by the Principal Investigator

## 10.2 Study Completion

The following data and materials are required before a study can be considered complete or terminated:

- All essential documents (e.g., curriculum vitae for the Principal Investigator and subinvestigator, U.S. FDA Form 1572 or equivalent (non-U.S.))
- Copies of protocol amendments, IRB/EC approval/notification, and signed and dated Protocol Amendment Acceptance Form(s) (*if applicable*)
- All data collection and query resolution complete Original, final SAE reports and all supporting documentation (i.e., discharge summaries, laboratory results)
- Original, final Pregnancy Information forms and all supporting documentation (*if applicable*)
- Complete and accurate investigational product accountability records and inventory log
- Laboratory results, clinical data, and all special test results from screening through the end of the study
- A summary of the study prepared by the principal investigator (IRB/EC summary close out letter is acceptable)

### **10.3 Informed Consent**

A sample ICF is provided as an attachment. In conformance with Federal Regulations governing informed consent, the STEMVAD study informed consent form that is given to the subject or authorized representative must be in a language understood by the patient or his/ her legal representative.

Prior to participation in the study, each patient must give written informed consent after having the study fully explained to him/her in the language that is most easily understood by the patient. All patients must be given the opportunity to ask questions and to have those questions answered to his/her satisfaction. All informed consent forms must be approved by the IRB before use and no patient may be consented unless such approval has been granted. All ICFs must be written in accordance with the current guidelines as outlined by GCP, and ICH. All informed consent forms must be signed and dated by the person providing explanation of the study and signed and dated by the patient or his/her legal representative prior to participation in this research study. A signed and dated copy of the informed consent form will be given to each patient.

### **10.4 Institutional Review Board**

A copy of the protocol, proposed ICFs, all written patient information, and any proposed advertising material must be submitted to the institution's IRB for written approval. No site may initiate study procedures/activities until such IRB approval had been granted in writing. A copy of the written IRB approval of the protocol and ICF must be received by the Sponsor of the trial before study supplies are shipped to the investigative site. The Investigator must submit and, where necessary, obtain IRB approval for all protocol amendments and changes to the ICF. If any investigator, co-investigator or sub-investigator participating in this study is a member of the IRB approving the study for the site, documentation must be provided by the IRB showing that the investigator did not vote on the approval of the study.

### **10.5 Study Monitoring Requirements**

The study site will be monitored by the Sponsor's designee. The Principal Investigator will permit said designee, the U.S. FDA or other regulatory agencies, Ethics Committees and the respective national or local

health authorities to inspect facilities and records relevant to this study, in accordance with GCP and the ICH. If the investigator is notified of an audit pertaining to this study by the U.S. FDA or other applicable regulatory authorities, the Investigator must notify the Sponsor immediately.

The Investigator must provide sufficient space and allocate sufficient time for the monitor to inspect subject source records, CRFs, investigational product accountability records, and regulatory documents.

## **10.6 Case Report Forms**

All CRFs will be filled out completely by designated personnel.

## **10.7 Source Data Documentation**

Study monitors will perform ongoing source data verification to confirm that critical protocol data (i.e., source data) transcribed on the CRFs by authorized site personnel are accurate, complete, and verifiable from source documents. Source documents are where subject data are recorded and documented for the first time. They include, but are not limited to, hospital records, clinical and office charts, laboratory notes, memoranda, subject diaries or evaluation checklists, pharmacy dispensing records, recorded data from automated instruments, copies of transcriptions that are certified after verification as being accurate and complete, microfiche, photographic negatives, microfilm or magnetic media, X-rays, subject files, and records kept at the pharmacy, laboratories, and medico-technical departments involved in a clinical trial. Source documents that are required to verify the validity and completeness of data transcribed on the CRFs must never be obliterated or destroyed. To facilitate source data verification, the investigator(s) and institution(s) must provide the sponsor direct access to applicable source documents and reports for trial-related monitoring, sponsor audits, and IRB review. The investigational site must also allow inspection by applicable regulatory authorities.

## **10.8 Investigational Product Accountability**

All investigational products required for completion of this study will be provided by CardioCell, LLC. The recipient will acknowledge receipt of the drug by returning the appropriate documentation form indicating

shipment content and condition. Damaged supplies will be replaced.

Accurate records of all study drug received at, dispensed from, returned to and disposed of by the study site will be recorded.

Investigational product will either be disposed of at the study site according to the study site's institutional standard operating procedure or returned to CardioCell, LLC with the appropriate documentation, as determined by the study site. If the study site chooses to destroy investigational product, the method of destruction must be documented.

CardioCell, LLC must evaluate and approve the study site's drug destruction standard operating procedure prior to the initiation of drug destruction by the study site.

#### **10.9 Retention of Records (for approval enabling studies only)**

United States FDA regulations (21 CFR §312.62[c]) and the ICH Guideline for GCP require that records and documents pertaining to the conduct of this study and the distribution of investigational drug, including CRFs, consent forms, laboratory test results, and medication inventory records, must be retained by the Principal Investigator for 2 years after the last marketing application approval in an ICH region or after at least 2 years have elapsed since formal discontinuation of clinical development of the investigational product. All state and local laws for retention of records also apply.

No records will be disposed of without written approval from the Sponsor. Written notification will be provided to Sponsor for transfer of any records to another party or moving them to another location.

## APPENDIX A: SCHEDULE OF ASSESSMENTS

Visit	Screening	Baseline	Randomization	Infusion 1	Post Infusion 1	Infusion 2	Post Infusion 2	Infusion 3	Post infusion 3	3 months	6 months	12 months	Early Term
Day	Days -12 to -11	Day -5 to -1		Day 0	1 Week	Day 30±7	1 Week	Day 60±7	1 Week	Day 90±7	Day 180±7	Day 360±7	
Informed Consent Form	X												
IV Infusion				X		X		X					
HIV Test	X												
Randomization			X										
Vital Signs and LVAD parameters**	X			X		X		X		X	X	X	X
Pulse Oximetry				X		X		X		X	X	X	X
Medical History	X			X		X		X		X	X	X	X
Concomitant medications	X			X		X		X		X	X	X	X
Physical Examination	X			X		X		X		X	X	X	X
6 minute walk test		X				X		X		X	X	X	X
Health Assessment, KCCQ, NYHA		X		X		X		X		X	X	X	X
12-lead ECG	X	X		X		X		X		X	X	X	X
Full 2D and 3 D Doppler transthoracic echocardiography with speckle-tracking		X				X		X		X	X	X	X
Zio patch (for patients who do not have an ICD)*		X		X		X		X		X	X	X	X
Gated blood pool SPECT ventriculography		X								X	X		X
ICD device check		X		X	X	X	X	X	X	X	X	X	X
CBC with differential				X		X		X		X	X	X	X
Serum Chemistry with BUN/Creatinine, LFT, total protein, albumin				X		X		X		X	X	X	X
LDH				X		X		X		X	X	X	X
HLA				X		X		X		X	X	X	
NT-proBNP				X		X		X		X	X	X	X
SST2				X		X		X		X	X	X	X
Troponin I				X		X		X					
IgA, IgE, IgG, and IgM				X		X		X		X	X	X	X

Biomarkers of immune response: CD14 CD163 CD40 CRP E-Selectin, Fas, (TNFRSF6/Apo-1) Fas Ligand, (TNFSF6) GCSF ICAM-1, (CD54) IL-1 alpha, (IL-1 F1), IL-1 beta IL-1 R4 IL-10 IL-12 p70 IL-13, IL-18 IL-2 IL-2 R alpha IL-4 IL-6, IL-8 Lipocalin-2 MCP-1 MCP-2 MIF, MIP-1 alpha MIP-1 beta Osteopontin PAI-1 Platelet Factor 4, Procalcitonin RAGE Resistin Thrombomodulin TNF alpha, TREM-1 Troponin I uPAR VCAM-1 VEGF-A, Antibody Isotype, Immune phenotyping, Proliferation Assay, In-vitro cytokine secretion, Cytokine assay (to be collected in 20 mL of blood—4 lavender tubes)				X	X	X	X	X	X	X	X	X	X
Total CK				X	X	X							
CK-MB				X	X	X							
Uric Acid				X	X	X		X	X	X			
HS-CRP				X	X	X		X	X	X			
Adverse Events				X	X	X	X	X	X	X	X		

‡ A coronary angiogram performed prior to LVAD implantation may be used to determine eligibility.

\*Zio patch recording or ICD device check must be completed prior to IV infusion.

\*\*Vital signs and LVAD parameters taken every 2 hours after infusion and pulse oximetry taken continuously for 2 hours after IV infusion. Vital signs include temperature, blood pressure, heart rate respiratory rate and weight, LVAD parameters include pump speed, power, flow and pulsatilityNeed continuous ECG monitoring during infusion

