5.2. Moreover, evidence suggests that MSCs residing in inflamed tissue will be detected more easily by the immune surveillance system, a change that would lead to shorter half-lives. Thus, Le Blanc et al demonstrated that undifferentiated MSCs express HLA class I but not class II molecules, leading to the conclusion these cells are less likely to be eliminated by the immune surveillance system. However, addition of IFNy for 48 hours induced greater than 90% of cells to express HLA class II molecules. This finding suggests that MSCs administered directly into an inflamed area, such as the myocardium in patients with AMI or HF, will begin expressing HLA class II molecules and will be more effectively eliminated by the immune surveillance system. In contrast, it appears that when MSCs are administered IV, where most of the cells reside in non-cardiac, non-inflamed tissue, they will be more immune evasive and persist longer, thereby having a greater opportunity to exert their beneficial effects on inflammation and myocardial function. In this regard, it is possible that prolonged persistence of MSCs, once injected, is not necessary to result in beneficial effects, but that efficacy results from a "hit-and-run" mechanism mediated by the secretion, through paracrine activities, of immunomodulatory factors during the initial days following MSC injection.

[figure not shown]

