## 4.2 Endpoints

### PRIMARY ENDPOINT

#### **Safety of MSCs assessed at the following time-intervals:**

Baseline and days 30, 60, 90, 180, and 360 post-initial infusion

1. Procedural complications
2. Vital signs
  - a. Temperature
  - b. Mean arterial blood pressure
  - c. Heart rate
  - d. Respiratory rate
  - e. Weight
  - f. LVAD parameters: Pump speed, flow, pulsatility and power
3. Uncontrolled systemic infection.
4. Hemodynamically unstable clinical arrhythmias that require appropriate defibrillator shock, anti-tachycardia pacing or initiation or escalation of antiarrhythmic medications.
5. Laboratory tests
  - a. Complete blood count (CBC)/ differential.
  - b. Comprehensive Metabolic Panel: Sodium, potassium, chloride, bicarbonate, blood urea nitrogen (BUN), creatinine, glucose, calcium, magnesium and liver function tests (ALT, AST, alkaline phosphatase, bilirubin and albumin)
  - c. Troponin-I.
  - d. Allosensitization (change in antibodies against HLA (panel reactive antibody test) from baseline for strong HLA antibody specificities (MFI>2000))
6. Electrocardiogram.
7. All-cause mortality. This will be reviewed by the DSMB. The LVAD population is a high risk group with very

high mortality, which will be taken into account when reviewing safety. Survival rate among HF patients with LVAD is 95% at 1 month, 81% at 1 year, 70% at 2 years, 59% at 3 years and 49% at 4 years. For patients enrolled within our study window, we would expect a 20% mortality rate in our patient population.

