## **SECONDARY ENDPOINT**

All secondary end points will be assessed pre-MSC infusion at days 0, 30, and 60, and also at days 90, 180, and 360. In addition, blood will be drawn 1 week after each infusion for potential biomarker analysis, depending on analysis of pre-infusion data. These 1-week post infusion blood samples will be frozen and stored.

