## 7.2.2 Assessments and treatment

Day 0 ± 7 Days, day 30 ± 7 Days and Day 60 ± 7 Days (day of first, second and third infusion, respectively)

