### Pre-infusion:

- Review and record any changes in medical history, including concomitant medications from before visit(s).
- Measure and record weight and vital signs (temperature, mean arterial blood pressure, weight, heart rate, respiratory rate, oxygen saturation, LVAD parameters: speed, power, flow, pulsatility) after subjects rest quietly in a supine or semi-recumbent position.
- Physical and cardiac examination.
- Draw and process blood samples for IgA, IgE, IgG, IgM
- Troponin, NT-pro Brain Natriuretic Peptide (NT-proBNP) and SST2.
- CK and CK-MB
- Zio patch or ICD assessment if not still on or done from baseline visit for the Zio patch patients
- Kansas City Cardiomyopathy Questionnaire (KCCQ). (30 and 60 day only)
- New York Heart Association (NYHA) Classification. (30 and 60 day only)
- 6 minute walk test (30 and 60 day only)
- Full 2D and 3D and Doppler transthoracic echocardiography with speckle-tracking (30 and 60 day only)
- Place an IV line in the upper extremity or hand with 0.9% sodium chloride running to keep the vein open
- CBC with differential
- CMP
- Uric Acid
- HLA and HS-CRP
- Biomarkers of inflammatory/immune response: A panel of inflammatory biomarkers: CD14, CD163, CD40, CRP, E-Selectin, Fas, (TNFRSF6/Apo-1), Fas Ligand (TNFSF6), GCSF, ICAM-1 (CD54), IL-1 alpha (IL-1 F1), IL-1 beta, IL-1 R4, IL-10, IL-12 p70, IL-13, IL-18, IL-2, IL-2 R alpha, IL-4, IL-6, IL-8,

Lipocalin-2, MCP-1, MCP-2, MIF, MIP-1 alpha, MIP-1 beta, Osteopontin, PAI-1, Platelet Factor 4, Procalcitonin, RAGE, Resistin, Thrombomodulin, TNF alpha, TREM-1, Troponin I, uPAR, VCAM-1, VEGF-A using a biomarker array kit and other markers as previously detailed using a biomarker array kit.

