### **7.3 Follow-up Assessments**

#### **One week post infusion (7 days ± 2 days)**

- Biomarkers of inflammatory/immune response: A panel of inflammatory biomarkers: CD14, CD163, CD40, CRP, E-Selectin, Fas, (TNFRSF6/Apo-1), Fas Ligand (TNFSF6), GCSF, ICAM-1 (CD54), IL-1

alpha (IL-1 F1), IL-1 beta, IL-1 R4, IL-10, IL-12 p70, IL-13, IL-18, IL-2, IL-2 R alpha, IL-4, IL-6, IL-8, Lipocalin-2, MCP-1, MCP-2, MIF, MIP-1 alpha, MIP-1 beta, Osteopontin, PAI-1, Platelet Factor 4, Procalcitonin, RAGE, Resistin, Thrombomodulin, TNF alpha, TREM-1, Troponin I, uPAR, VCAM-1, VEGF-A using a biomarker array kit and other markers as previously detailed using a biomarker array kit.

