#### **Day 90, 180, and 360 ( $\pm 7$ ) days post initial infusion**

- Measure and record vital signs
- 12-lead ECG
- Pulse Oximetry
- Zio patch or ICD assessment
- Record all-cause mortality, admission for worsening HF and all-cause admissions, AEs and concomitant medication use
- Physical and cardiac examination
- Changes in medical history
- Clinical labs: serum chemistry including BUN & creatinine, CBC with differential, LFTs, total protein, albumin and LDH.
- HS-CRP
- Cardiac Biomarkers: NT-pro Brain Natriuretic Peptide (NT-proBNP) and ST 2
- Biomarkers of immune response: A panel of inflammatory biomarkers: CD14, CD163, CD40, CRP, E-Selectin, Fas, (TNFRSF6/Apo-1), Fas Ligand (TNFSF6), GCSF, ICAM-1 (CD54), IL-1 alpha (IL-1 F1), IL-1 beta, IL-1 R4, IL-10, IL-12 p70, IL-13, IL-18, IL-2, IL-2 R alpha, IL-4, IL-6, IL-8, Lipocalin-2, MCP-1, MCP-2, MIF, MIP-1 alpha, MIP-1 beta, Osteopontin, PAI-1, Platelet Factor 4, Procalcitonin, RAGE, Resistin, Thrombomodulin, TNF alpha, TREM-1, Troponin I, uPAR, VCAM-1, VEGF-A using a biomarker array kit using a biomarker array kit. Antibody Isotype assays, leukocyte cytokine secretory assays, and leukocyte cytotoxic effects toward MSCs. Blood sample for IgA, IgE, IgG, IgM,

- Kansas City Cardiomyopathy Questionnaire (KCCQ)
- New York Heart Association (NYHA) Classification
- 6 minute walk test
- Full 2D and 3 D and Doppler transthoracic echocardiography with speckle-tracking.
- Gated blood pool SPECT ventriculography (only 90 and 180 days)
- Uric Acid
- HLA

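### With infusions and visits in window, no blood count, chemistry, liver test or LDH is scheduled sooner than 16 days after an infusion, although blood is already drawn at one week

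*Combined protocol and SAP*

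**What the plan says.** Section 4.2 sets the primary safety time points as "Baseline and days 30, 60, 90, 180, and 360 post-initial infusion". Item 5 of that endpoint covers the blood count with differential, a metabolic panel with liver tests, troponin I and HLA antibodies. LDH is not named there, but section 7.1 includes it in serum chemistry and Appendix A gives it a row.

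In Appendix A the rows for CBC, LDH and "Serum Chemistry with BUN/Creatinine, LFT, total protein, albumin" carry marks at infusions 1, 2 and 3, at months 3, 6 and 12, and at early termination. All three one-week post-infusion columns are blank for these rows.

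The body text agrees. Section 7.2.2 puts "CBC with differential" and the metabolic panel in its pre-infusion list, and its post-infusion list has no blood test. At days 90, 180 and 360, section 7.3 asks for "Clinical labs: serum chemistry including BUN & creatinine, CBC with differential, LFTs, total protein, albumin and LDH". For the visit one week after an infusion, the same section lists only the inflammatory and immune biomarker panel.

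That visit does involve a blood draw. The Subject Participation section schedules days 7, 37 and 67 (±2 days), and section 4.2 says "blood will be drawn 1 week after each infusion for potential biomarker analysis", with these samples frozen and stored.

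Section 9.2 summarises laboratory change from baseline to the next infusion or follow-up visit.

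**The concern.** The trial exists mainly to learn whether repeated infusions are safe. Background 8 accepts that the safety of multiple injections is not yet definitively established, and Background 9 calls this the first multi-injection study in cardiac patients. The Background also says that most intravenous cells lodge outside the heart, naming the lungs, liver and spleen in one place and the kidneys in another. Liver tests and creatinine are the routine checks on two of those organs.

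Under the schedule, a fall in counts or a rise in transaminases, creatinine or LDH that appeared after each dose and settled without symptoms before the next visit would leave no trace in the planned data. The tables in 9.2 could then look alike in the two arms because nothing was measured in that interval. Nor would there be a scheduled result on these tests from one infusion before the day of the next. The gap is in what is collected, so no choice of analysis can repair it later.

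**Working it through.** The plan states no interval between infusion and laboratory sample, and no power calculation bears on the point, so there is no figure to reproduce. The check is arithmetic on the visit windows.

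**Inputs**
- Infusions: section 7.2.2 gives "Day 0 ± 7 Days, day 30 ± 7 Days and Day 60 ± 7 Days". Infusion 2 is therefore on days 23 to 37 and infusion 3 on days 53 to 67.
- Day 0: Appendix A prints it without a window, and 4.2 counts days from the initial infusion, so the main reading puts infusion 1 on day 0. The alternative lets it move by ±7 days.
- Next laboratory visit after infusion 3: day 90 ±7, that is days 83 to 97.
- One-week visit: 7 ±2 days after each infusion.
- Infusion-day samples are taken before dosing. Section 7.2.2 does not name LDH, but it lists no blood test after the infusion.

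**Formula**
Shortest gap = earliest day of the next laboratory visit − latest day of the infusion. Longest gap = latest day of that visit − earliest day of the infusion.

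**Results with everything in window**

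| Interval | Shortest (days) | Longest (days) | Nominal (days) |
|---|---|---|---|
| Infusion 1 to sample before infusion 2 | 23 − 0 = 23 | 37 − 0 = 37 | 30 |
| Same, if day 0 moves ±7 | 23 − 7 = 16 | 37 + 7 = 44 | 30 |
| Infusion 2 to sample before infusion 3 | 53 − 37 = 16 | 67 − 23 = 44 | 30 |
| Infusion 3 to day 90 sample | 83 − 67 = 16 | 97 − 53 = 44 | 30 |

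**Out-of-window cases**
- Section 5.2 lets a missed infusion be given later, with infusion 3 following infusion 2 by 30 days but ahead of the day 90 (plus window) evaluation. If infusion 2 falls on day 45, 50, 55 or 59, infusion 3 falls on day 75, 80, 85 or 89. That is 15, 10, 5 or 1 days before a day 90 visit. At the edge, infusion 3 on day 96 and a visit on day 97 also give 1 day.
- Section 7.4 repeats these tests at early termination, with no minimum time since the last infusion.

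These values arise by chance, at no common time point in the two arms.

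**With the tests added to the one-week draw**
First result at 7 − 2 = 5 to 7 + 2 = 9 days. Extra panel sets: 3 per subject × 30 subjects = 90 at most.

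**The case against.** The case for leaving the schedule alone is fair. For these tests, sections 4.2, 7.2.2, 7.3 and Appendix A agree, so this is a design choice and nothing has to be reconciled. The experience cited in Background 7 and 8 is reassuring: the same product in an earlier trial of 23 patients, a meta-analysis of systemic administration, and four monthly infusions in COPD. There is other monitoring too: ECG and oximetry during infusion and for 2 hours afterwards, at least a day between the first five subjects, adverse event questioning at every contact, and ongoing DSMB review. An abnormal laboratory finding counts as an adverse event.

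This stands, and it narrows the gap to changes that are silent and resolve unaided. It does not close the gap. Questioning cannot find a laboratory change that nobody measured, and the DSMB cannot review results that do not exist.

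Two stronger readings are tempting, and the documents do not support them.

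- A reader might infer that every post-dose safety laboratory value is at least 16 days old. Late infusions, early termination visits and unscheduled tests can give earlier ones. Troponin I, also in item 5, is on the biomarker panel collected at one week, although those samples are stored for possible later analysis. The column positions of the CK, CK-MB, uric acid and hs-CRP rows cannot be read with confidence in the copy reviewed, so nothing here rests on them.
- A reader might infer that any acute toxicity will be over by the time of sampling. Background 5.2 does speak of "immunomodulatory factors during the initial days following MSC injection", but as a possibility and about benefit. Background 9 describes cells lasting to about day 20. No toxicity time course is given, and the answer depends on what is assumed. With an assumed half-life of 7 days, 2^(−16/7) = 0.205 of a peak at the time of infusion would remain at day 16 and 2^(−30/7) = 0.051 at day 30. With 3 days, the figures are 2^(−16/3) = 0.025 and 2^(−30/3) = 0.001.

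**Conclusion.** The concern holds for CBC, serum chemistry, liver tests and LDH, with infusions and visits in window. None of these is scheduled sooner than 16 days after an infusion. The nominal gap is 30 days and the longest is 44; after infusion 1 the range is 23 to 37 days if day 0 is the initial infusion. The planned results on these tests therefore cannot show a silent, transient change in the first two weeks after a dose.

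This rests on the printed windows and on the Appendix A rows, which the body text supports; it needs no assumption about biology. It does not show that such a change will occur or that the existing schedule is unsafe. It is a cheap improvement to a trial whose primary question is the safety of repeated dosing.

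**What to change.** - In Appendix A and section 7.3, add CBC with differential, serum chemistry with liver tests, and LDH to the existing draw one week after each infusion (days 7, 37 and 67, ±2). Run them at the time; do not freeze them.
- In section 4.2, add those days to the time points for safety item 5, and say whether LDH belongs to that item or is reported beside it.
- In section 9.2, summarise the change from the pre-infusion value to the one-week value by arm and infusion number. A within-subject change is needed because exclusion 14 admits patients with ALT or AST up to 3 times normal.

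The cost is a protocol amendment, one extra small tube at a venipuncture already scheduled, and laboratory charges for up to 90 routine panel sets. No new visit, staff or venipuncture is needed, and no dose or clinical rule changes.
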